## Section: 7.4 Laboratory Assessments

### Table 2, footnote C

**Add:**

c At screening if the subject is positive for hepatitis B core antibody, the confirmatory reflex testing will be performed using HBV DNA PCR.

## Section: 9.2.1 Reporting Procedures for Adverse Events That do not Meet Serious Criteria

### Paragraph 3, sentence 1

**Replace:**

The adverse event grading scale used will be the Common Toxicity Criteria Version 2.

**With:**

The adverse event grading scale used will be the Common Toxicity Criteria Version 4.

## Section: 11.1 Informed Consent

### Paragraph 1, sentence 2

**Replace:**

Updates to the template are to be communicated formally in writing from the Amgen Clinical Study Manager to the investigator.

**With:**

Updates to the template are to be communicated formally in writing from the Amgen **Global Clinical Trial** Manager to the investigator.

## Section: Appendix A

### Adverse Event Grading Scale

**Replace:**

The Common Toxicity Criteria Version 2.0 is available at the following link:

[http://ctep.cancer.gov/protocolDevelopment/electronic\\_applications/docs/ctcv20\\_4-30-992.pdf](http://ctep.cancer.gov/protocolDevelopment/electronic_applications/docs/ctcv20_4-30-992.pdf)

**With:**

The Common Toxicity Criteria Version 4.0 is available at the following link:

[http://ctep.cancer.gov/protocolDevelopment/electronic\\_applications/ctc.htm](http://ctep.cancer.gov/protocolDevelopment/electronic_applications/ctc.htm)

## Amendment 2

**Protocol Title: A Multicenter Double-Blind, Randomized Controlled Study of Etanercept and Methotrexate in Combination or as Monotherapy in Subjects With Psoriatic Arthritis**

Amgen Protocol Number (Etanercept) 20130207

EudraCT Number 2014-004869-24

Original Protocol:	29 July 2014
Amendment 1 Date:	20 May 2015
Superseding Amendment 1 Date:	09 July 2015
Amendment 2 Date:	30 October 2015

### **Rationale:**

The protocol is being amended to be consistent with international regulations and requirements.

## Superseding Amendment 1

#### Rationale:

The protocol is being amended to:

- Provide updated pregnancy and contraception language. Updated language for pregnancy and contraception became available immediately following approval of Amendment 1, thus, a superseding amendment to Amendment 1 was created to include the updated language. Changes related to both Amendment 1 and Superseding Amendment 1 are detailed below. Likewise, changes in bold include all changes from Amendment 1 and Superseding Amendment 1.
- Provide clarification for reporting hepatotoxicity as a serious adverse event
- Clarify indications regarding use of etanercept in the US and Canada, and add medical information phone number as a reference for countries other than US and Canada
- Update and clarify inclusion/exclusion criteria regarding tender and swollen joint counts, minimum number of weeks required for stable dosing of NSAIDs, excluded medications, and minimum number of months since use of excluded medications.
- Provide clarification regarding exclusion criteria to expand wording related to substances of abuse
- Provide clarifications regarding joint assessments, to strengthen wording related to continuity of assessors in the study, and allowing for assessments by principal investigators
- Add folic acid and folinic acid dosing information
- Add additional information regarding laboratory assessments used to determine subject eligibility
- Clarify process for when inadvertent unblinding occurs
- Provide updates throughout to reflect the number of global participating sites
- Clarify formulation of methotrexate used for rescue therapy
- Add the EudraCT number
- Update the Key Sponsor Contact
- Provide an updated eSAE example form, pregnancy worksheet, and lactation worksheet
- Make minor corrections and clarifications throughout

Appendix A. Technical Detail and Supplemental Information Regarding
Statistical Procedures and Programs 39

Appendix B. Code Fragments..... 53

Appendix C. Reference Values/Toxicity Grades 56

Table of Abbreviations

| Abbreviation or Term | Definition/Explanation |
|----------------------|--|
| ACR | American College of Rheumatology |
| ANCOVA | Analysis of covariance |
| BMI | body mass index |
| BSA | body surface area |
| CDAI | Clinical Disease Activity Index |
| CMH | Cochran Mantel Haenszel |
| CRP | C-reactive protein |
| DAS28-CRP | Disease Activity Score (28 Joints) using CRP |
| DAPSA | Disease Activity index for Psoriatic Arthritis |
| DMARD | Disease Modifying Anti-rheumatic Drug |
| EOS | End of Study |
| ES | Erosion Score |
| ET | Early Termination |
| HAQ-DI | Health Assessment Questionnaire Disability Index |
| ICH | International Conference on Harmonisation |
| IP | Investigational product |
| IPD | Important protocol deviation |
| ITT | Intent-to-treat |
| JSN | Joint Space Narrowing |
| LOCF | Last observation carried forward |
| LDI | Leeds Dactylitis Index |
| MDA | minimal disease activity |
| mNAPSI | Modified Nail Psoriasis Severity Index |
| mTSS | van der Heijde modified Total Sharp Score |
| MI | Multiple imputation |
| NRI | Non-responder imputation |
| PASDAS | Psoriatic Arthritis Disease Activity Score |
| PRO | patient reported outcome |
| PsA | psoriatic arthritis |
| QW | Weekly |
| SAP | statistical analysis plan |
| SDAI | Simplified Disease Activity Index |
| SF-36 v2 | Medical Outcomes Health Survey Short Form 36 items version 2 |

| Abbreviation or Term | Definition/Explanation |
|-----------------------------|---|
| SPARCC | Spondyloarthritis Research Consortium of Canada |
| sPGA | Static Physician Global Assessment |
| TNF | tumor necrosis factor |
| VAS | visual analog scale |
| VLDA | Very Low Disease Activity |

1. Introduction

The purpose of this statistical analysis plan (SAP) is to provide details of the statistical analyses that have been outlined within the protocol amendment 3 for etanercept Study 20130207 dated 31 August 2016. The scope of this plan includes the final analysis that is planned and will be executed by the Biostatistics department unless otherwise specified.

2. Objectives

2.1 Primary Objective

To evaluate the efficacy of etanercept plus methotrexate therapy and etanercept monotherapy compared to methotrexate monotherapy, in subjects with psoriatic arthritis (PsA) as measured by the proportion of subjects achieving an American College of Rheumatology (ACR) 20 response at week 24.

2.2 Key Secondary Objective

To evaluate the efficacy of etanercept plus methotrexate therapy and etanercept monotherapy compared to methotrexate monotherapy as measured by the proportion of subjects achieving minimal disease activity (MDA) at week 24.

2.3 Other Secondary Objectives

To evaluate the efficacy of etanercept plus methotrexate therapy and etanercept monotherapy compared to methotrexate monotherapy on the following:

- Other measures of arthritis activity
- Measures of non-arthritic PsA disease activity
- Key patient reported outcomes (PRO) related to physical function and quality of life

2.4 Safety Objectives

To evaluate the safety of etanercept and methotrexate.

2.5 Exploratory Objectives

To evaluate the efficacy of etanercept plus methotrexate therapy and etanercept monotherapy compared to methotrexate monotherapy on the following:

- Other measures of disease activity including the skin
- Other PROs
- Inhibition of radiographic progression as measured by the van der Heijde modified Total Sharp score (mTSS) for PsA
- To investigate potential biomarkers of disease activity and response to etanercept
- To investigate the effects of genetic variation in disease genes and drug target genes on PsA and/or subject response to etanercept

3. Study Overview

3.1 Study Design

This is a phase 3, multicenter, randomized, double-blind controlled study in subjects with active PsA naïve to biologics and with no prior use of methotrexate for the treatment of PsA. The study will consist of a 30-day screening period, a 48-week randomized double-blind treatment period, and a 30-day safety follow-up period.

Approximately 840 subjects will be randomly assigned in a 1:1:1 ratio to one of three treatment groups (280 per arm):

- Etanercept 50 mg weekly by subcutaneous injection plus oral methotrexate 20 mg weekly
- Etanercept 50 mg weekly by subcutaneous injection plus oral placebo for methotrexate
- Oral methotrexate 20 mg weekly plus placebo for etanercept.

At or after week 24, subjects who have an inadequate response will receive rescue therapy with etanercept plus methotrexate until the end of the treatment period.

Inadequate response is defined by having < 20% improvement in their tender joint counts and < 20% improvement in their swollen joint counts from baseline at or after week 24. Inadequate response may be assessed at a regularly scheduled visit or at a disease assessment visit. All subjects that initiate rescue treatment must complete a disease assessment follow-up visit 4 weeks later to monitor for labs.

3.2 Sample Size

A total of 840 subjects will be enrolled in the study and randomized in a 1:1:1 ratio to etanercept plus methotrexate therapy, etanercept monotherapy, and methotrexate monotherapy.

To preserve the family-wise 2-sided type one error rate at 0.05 for the multiple comparisons of the etanercept plus methotrexate therapy and etanercept monotherapy groups with methotrexate monotherapy, a Bonferroni-based gatekeeping chain procedure ([Burman et al 2009](#) and [Millen et al 2011](#)) will be used to determine statistical significance for the primary and key secondary endpoints as described in [Section 10.5.1](#). This procedure will split alpha of 0.05 equally to test in parallel the primary and key secondary endpoints (ACR 20, MDA) for etanercept plus methotrexate therapy vs. methotrexate monotherapy and etanercept monotherapy vs. methotrexate monotherapy sequentially within each parallel path. If one of the parallel paths rejects both hypotheses sequentially, and the other parallel path has at least one hypothesis not

rejected, then the unspent alpha of 0.025 from the successful path will be propagated to the hypotheses in the other path to re-test them sequentially at a level of 0.05.

The sample size is based on the adequacy to evaluate the efficacy of etanercept monotherapy compared with methotrexate monotherapy as measured by the primary endpoint of ACR 20 response at week 24 at a significance level of 0.025 based on the Bonferroni-based gatekeeping chain procedure.

There are no published studies of etanercept monotherapy versus methotrexate monotherapy for the treatment of PsA. Therefore for the purpose of this study the assumed response rates for ACR 20 for the etanercept monotherapy and methotrexate monotherapy arms are derived from separate studies. In the etanercept PsA pivotal phase 3 study (20021630 Study) the ACR 20 response rate at week 24 was 50% for the etanercept arm. However, subjects were allowed to be on a stable dose of methotrexate at study entry. Assuming a methotrexate naïve population would respond better, the response rate for the etanercept monotherapy arm in this planned phase 3 study is assumed to be 60%.

In a recent randomized placebo-controlled trial of methotrexate monotherapy in PsA ([Kingsley et al, 2012](#)) the ACR 20 response rate for the methotrexate monotherapy arm was 34%. However, the dose of methotrexate was 15 mg QW. Assuming a higher dose of methotrexate (ie, 20 mg QW) would yield better responses, the response rate for the methotrexate monotherapy arm in this planned phase 3 study is assumed to be 44%.

Therefore, in order to detect a difference of 16% between the etanercept monotherapy and methotrexate monotherapy arms, using a two-sided Chi-square test at a significance level of 0.025 and 90% marginal power, each treatment arm will have approximately 280 subjects adjusting for an anticipated 10% dropout.

This sample size will provide marginal power > 90% to detect a treatment difference in ACR 20 response at week 24 between the etanercept plus methotrexate therapy arm and the methotrexate monotherapy arm at a two-sided 0.025 significance level. As previously mentioned, the ACR response rate at week 24 is assumed to be 44% for the methotrexate monotherapy arm. The ACR response rate at week 24 for the etanercept plus methotrexate therapy arm is assumed to be 5% higher than the etanercept monotherapy arm (ie, 65%). This is based on a longitudinal observational study assessing the role of TNF-inhibitor plus methotrexate combination therapy versus TNF-inhibitor monotherapy ([Fagerli et al, 2014](#)).

In addition, this sample size will provide marginal power > 90% to detect treatment differences in MDA response at week 24 between both etanercept arms and the methotrexate arm at a two-sided 0.025 significance level, assuming response rates of 15%, 30%, and 35% for the methotrexate monotherapy, etanercept monotherapy, and etanercept plus methotrexate therapy arms, respectively. In recent PsA trials, the MDA 24-week response rates for the placebo arm range from 3 to 7% (Coates et al, 2010a; Kavanaugh et al, 2013). Therefore, for the methotrexate monotherapy arm, the response rate is assumed to be higher at 15%. In the pivotal phase 3 randomized placebo-controlled trial of etanercept in PsA, the MDA response rate for the etanercept monotherapy arm is estimated to be approximately 20% at week 24 (data on file). For a methotrexate naïve population, the response rate is assumed to be higher at 30%. In addition, the etanercept plus methotrexate therapy arm is assumed to have a 5% improvement over the etanercept monotherapy arm.

4. Study Endpoints and Covariates

4.1 Study Endpoints

4.1.1 Primary Endpoint

- ACR 20 response at week 24

4.1.2 Key Secondary Endpoint

- MDA response at week 24

4.1.3 Other Secondary Endpoints

- ACR 20 response at all measured time points other than week 24
- MDA response at all measured time points other than week 24
- Psoriatic Arthritis Disease Activity Score (PASDAS) at all measured time points and change from baseline at all measured time points
- ACR 50, ACR 70, and components of ACR at all measured time points
- Simplified Disease Activity Index (SDAI) and change from baseline at all measured time points
- Clinical Disease Activity Index (CDAI) and change from baseline at all measured time points
- Disease activity score (28 joint) using the C-reactive protein formula (DAS28-CRP) and change from baseline at all measured time points
- Health Assessment Questionnaire Disability Index (HAQ-DI) score and change from baseline at week 24
- Short Form (36) Health Survey Version 2 (SF-36v2) (MCS and PCS) score and change from baseline at week 24

For subjects with non-zero mNAPSI at baseline,

- mNAPSI and change from baseline at week 24
- achievement of mNAPSI = 0 at week 24

For subjects with non-zero Leeds Dactylitis Index (LDI) at baseline,

- LDI and change from baseline at week 24
- achievement of LDI = 0 at week 24

For subjects with non-zero Spondyloarthritis Research Consortium of Canada (SPARCC) enthesitis at baseline,

- SPARCC enthesitis score and change from baseline at week 24
- achievement of SPARCC score = 0 at week 24

For subjects with involved body surface area (BSA) $\geq 3\%$ at baseline, $< 3\%$ at baseline, and $\geq 3\%$ but $< 10\%$ at baseline, $\geq 10\%$ at baseline:

- Static Physician Global Assessment (sPGA) categorical summary by 0,1,2,3,4,5 at week 24
- sPGA continuous summary at week 24
- sPGA of 0 or 1 (yes/no) at week 24
- sPGA one grade improvement from baseline at week 24
- sPGA two grade improvement from baseline at week 24
- BSA, change and percent improvement from baseline at week 24

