#### 4.1 Inclusion and Exclusion Criteria

##### 4.1.1 Inclusion Criteria

101. Subject has provided informed consent prior to initiation of any study-specific activities/procedures.
102.  $\geq 18$  years of age at screening
103. subject has had a diagnosis of PsA by the Classification Criteria for Psoriatic Arthritis (CASPAR) criteria
104. subject has  $\geq 3$  tender and  $\geq 3$  swollen joints (as part of a 68/66 joint count) at screening and at baseline
105. subject has an active psoriatic skin lesion (at least one psoriatic plaque approximately 2 cm or more in diameter)
106. subject is naïve to etanercept and any other biologic for the treatment for PsA or psoriasis
107. subject has no prior use of methotrexate for PsA. Prior treatment with methotrexate is allowed if indicated for psoriasis as long as discontinuation was not due to toxicity or intolerance and treatment discontinued  $\geq 6$  months prior to initiation of investigational product
108. for subjects receiving non-steroidal anti-inflammatory drugs (NSAIDs) (including as needed use [PRN]): the dose must be stable for  $\geq 2$  weeks prior to initiation of investigational product
109. for subjects receiving oral corticosteroids: the dose must be stable (not to exceed the equivalent of 10 mg of prednisone per day) for  $\geq 4$  weeks prior to initiation of investigational product
110. negative test for hepatitis B surface antigen, hepatitis B core antibody and hepatitis C antibody
111. no known history of active tuberculosis
112. National guidelines should be followed for appropriate tuberculosis screening in the setting of anti-TNF therapy, including a minimum of:
  - subject has a negative test for tuberculosis during screening defined as either:
    - negative purified protein derivative (PPD) ( $< 5$  mm of induration at 48 to 72 hours after test is placed) OR
    - negative Quantiferon test.

subjects with a positive PPD and a history of Bacillus Calmette-Guérin vaccination are allowed with a negative Quantiferon test.

subjects with a positive PPD test (without a history of Bacillus Calmette-Guérin vaccination) or subjects with a positive or indeterminate Quantiferon test are allowed if they have ALL of the following:

- no symptoms per tuberculosis worksheet provided by Amgen Inc.
- documented history of a completed course of adequate treatment or prophylaxis per local standard of care prior to the start of investigational product

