lateral epicondyle (left and right), supraspinatus insertion into greater tuberosity of humerus (left and right), greater trochanter (left and right), quadriceps insertion into superior border of patella (left and right), patellar ligament insertion into inferior pole of patella or tibial tubercle (left and right), Achilles tendon insertion into calcaneum (left and right), plantar fascia insertion into calcaneum (left and right). A higher count represents greater enthesitis burden.

Details of the scoring algorithm are described in [Appendix A](#).

Static Physician Global Assessment of Psoriasis (sPGA)

The static Physician Global Assessment of psoriasis (sPGA) evaluates the physician's global assessment of the subject's psoriasis based on severity of induration, scaling, and erythema. The sPGA is assessed on a scale of 0 (clear) to 5 (severe).

Swollen Joint Count

A score that assesses the presence or absence of swelling in 66 joints. Details of the scoring algorithm are described in [Appendix A](#).

Tender Joint Count

A score that assesses the presence or absence of tenderness in 68 joints. Details of the scoring algorithm are described in [Appendix A](#).

Treatment Emergent AE

A treatment emergent AE is defined as an event that occurs on or after the initiation of the IP and prior to the EOS date (ie, 30 days after last dose of IP). It is determined by the pre-treatment flag (ie, AE.AEPRETRT NE 'Y') on the Events CRF with a start date up to 30 days after the end of investigational product or the End of Study date, whichever is earlier.

Van der Heijde Modified Total Sharp Score (mTSS)

A method for assessing erosions and joint space narrowing of the hands and feet based on the Sharp-van der Heijde method in rheumatoid arthritis. The method is adapted for evaluation of PsA by including the distal interphalangeal joints of the hand and scoring not only for erosions and joint space narrowing but also for subluxation, ankylosis, gross osteolysis, and pencil in cup phenomena. The maximum possible total score is 528.

A higher score represents worse destruction. Details of the scoring algorithm are described in [Appendix A](#).

Very Low Disease Activity (VLDA)

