7.2 Psoriasis Efficacy Analysis Set

The psoriasis efficacy analysis set will include all randomized subjects with baseline BSA $\geq 3\%$. Subjects will be analyzed according to their randomized treatment group. Analyses of psoriasis efficacy endpoints (eg, sPGA, BSA) will be based on the psoriasis efficacy analysis set.

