10.5.2 Analyses of Other Secondary Efficacy and Selected Exploratory Endpoints

The analysis of the following secondary and exploratory endpoints at week 24 will be performed using the LDI analysis set for LDI endpoints, SPARCC Enthesitis analysis set for SPARCC endpoints, mNAPSI analysis set for mNAPSI endpoints, and the full analysis set for the other efficacy endpoints unless otherwise specified:

- LDI change from baseline at week 24 (LDI analysis set)
- Achievement of LDI=0 at week 24 (LDI analysis set).
- SPARCC change from baseline at week 24 (SPARCC analysis set)
- Achievement of SPARCC=0 at week 24 (SPARCC analysis set)
- mNAPSI change from baseline at week 24 (mNAPSI analysis set)
- Achievement of mNAPSI=0 at week 24 (mNAPSI analysis set)
- PASDAS change from baseline at week 24
- DAS28-CRP change from baseline at week 24
- SDAI change from baseline at week 24
- CDAI change from baseline at week 24
- VLDA at week 24
- DAPSA change from baseline at week 24

For binary endpoints, treatment effect will be tested using the stratified CMH test with BMI and prior non-biologic DMARD use as the stratification factors. For continuous endpoints that exhibit normal distribution, ANCOVA model will be used. The model will include treatment groups and baseline BMI and prior non-biologic DMARD as covariates. For continuous endpoints that are not normally distributed, endpoint data will be first transformed to their joint ranks and then further transformed by the Van der Waerden transformation to normalize them before applying the ANCOVA model. The significance level for other secondary endpoints will be 0.05 without adjusting for multiplicity and p-values will therefore be treated as a descriptive statistic only. All the testing will be performed for endpoints at week 24 and methotrexate monotherapy group will be the reference group.

Analyses to other secondary endpoints will be summarized descriptively only. sPGA and BSA summary analyses will be performed using psoriasis efficacy analysis set and subgroups of subjects with the baseline BSA < 3%, > = 3% but < 10%, and > = 10%.

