10.6.5 Exposure to Concomitant Medication

A summary of all concomitant medications reported may be provided by preferred term as coded by the World Health Organization Drug (WHODRUG) dictionary.

11. Changes From Protocol-specified Analyses

Changes are made only for secondary or exploratory endpoints. The changes are instituted to adopt the standardized ways to report the efficacy endpoints in PsA trials.

The changes to LDI, SPARCC, and mNAPSI are made to focus on relevant sub-populations for analysis. Modeling analyses described in [Section 10.5.2](#) will be

limited to selected secondary endpoints at week 24 only, for the inclusion in CSR.
Further analyses may be performed later on an ad hoc basis.

Specifically, the changes are as follows:

1. These analysis sets are added to the SAP because they are more relevant to the purpose of the analyses focusing on the subpopulations with disease progression.

Leeds Dactylitis Index (LDI) Analysis Set

The leeds dactylitis index analysis set will consist of all the randomized subjects with non-zero LDI at baseline. Subjects will be analyzed according to their randomized treatment group. Analyses of LDI efficacy endpoints will be based on the leeds dactylitis index analysis set.

Modified Nail Psoriasis Severity Index (mNAPSI) Analysis Set

The mNAPSI analysis set will consist of all the randomized subjects with non-zero mNAPSI at baseline. Subjects will be analyzed according to their randomized treatment group. Analyses of mNAPSI efficacy endpoints will be based on this analysis set.

SPARCC Enthesitis Analysis Set

The SPARCC Enthesitis Analysis Set will consist of the randomized subjects with non-zero SPARCC enthesitis at baseline. Subjects will be analyzed according to their randomized treatment group. Analyses of SPARCC efficacy endpoints will be based on the SPARCC Enthesitis analysis set.

2. Modification of the other secondary endpoints limited to specific subpopulation in in [Section 4.1.3](#) as follows:

For subjects with non-zero mNAPSI at baseline,

- mNAPSI and change from baseline at week 24
- achievement of mNAPSI = 0 at week 24

For subjects with non-zero Leeds Dactylitis Index (LDI) at baseline,

- LDI and change from baseline at week 24
- achievement of LDI = 0 at week 24

For subjects with non-zero Spondyloarthritis Research Consortium of Canada (SPARCC) enthesitis at baseline,

- SPARCC enthesitis score and change from baseline at week 24
- achievement of SPARCC score = 0 at week 24

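### The sPGA 0/1 and grade-improvement rates are reported in sets chosen by BSA alone, so they include subjects who start at sPGA 1 or below: these already meet 0/1 and cannot improve two grades

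*SAP*

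**What the plan says.** SAP 4.1.3 gives a list of skin summaries for subjects grouped by baseline BSA (at least 3%, below 3%, 3% to below 10%, at least 10%). The list includes "sPGA of 0 or 1 (yes/no) at week 24", one-grade improvement, "sPGA two grade improvement from baseline at week 24", a 0-5 categorical summary and a continuous summary. SAP 4.1.5 repeats it for the other visits.

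The analysis populations use area only. SAP 7.2: "The psoriasis efficacy analysis set will include all randomized subjects with baseline BSA" of at least 3%. SAP 10.5.2: "sPGA and BSA summary analyses will be performed using psoriasis efficacy analysis set and subgroups of subjects with the baseline BSA < 3"% and the two higher BSA bands. Protocol 4.1.1, criterion 105, requires this of the skin at entry: "subject has an active psoriatic skin lesion (at least one psoriatic plaque approximately 2 cm or more in diameter"). No section sets a minimum sPGA.

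On the scale itself, SAP 6.6 says: "The sPGA is assessed on a scale of 0 (clear) to 5 (severe"). It and Protocol 7.3.9.1 base the grade on induration, scaling and erythema.

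The nail, dactylitis and enthesitis endpoints in SAP 4.1.3 are handled differently. The nail entry begins "For subjects with non-zero mNAPSI at baseline", and LDI and SPARCC carry the same condition. SAP Section 11 gives the reason: "The changes to LDI, SPARCC, and mNAPSI are made to focus on relevant sub-populations for analysis".

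sPGA is not on the SAP 10.5.2 list of tested endpoints. It falls under the remaining endpoints, which are only summarised descriptively.

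**The concern.** A responder rate is easiest to read when everyone in the denominator could respond and nobody had already met the criterion. Here neither is assured. The sPGA grades severity, not extent, so a BSA cut-off does not exclude a subject with mild lesions. The SAP also adds a BSA < 3% group, which Protocol 10.1.1.3 did not have for sPGA, and low starting grades are most plausible there.

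A subject who starts and stays at sPGA 1 counts as a success on 0/1 and as a failure on two-grade improvement, with no change in the skin. What is at stake is how the skin rates read: the 0/1 rates are likely raised, the two-grade rate has a ceiling below 100%, and the absolute differences between arms may look smaller than they are among subjects with room to respond.

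**Working it through.** **Inputs.** From the documents: the 0-5 scale, the BSA-only sets, and no minimum sPGA. The documents give no sPGA response rate, no baseline sPGA distribution and no sPGA power, so there is no sPGA figure of the plan's own to reproduce. The sample-size figures concern ACR 20 and MDA and do not bear on this point. All rates below are assumptions for illustration.

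**Step 1: what the scale allows.** A subject at baseline grade b can improve by at most b grades.

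| Baseline sPGA | Meets 0/1 at entry | One-grade gain possible | Two-grade gain possible |
|---|---|---|---|
| 0 | yes | no | no |
| 1 | yes | yes | no |
| 2 to 5 | no | yes | yes |

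Subjects at 0 or 1 are certain failures for two-grade improvement. They are not certain successes for 0/1, because they can be at 2 or above by week 24.

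**Step 2: formulas.** Let f be the share of a BSA set with baseline sPGA of 1 or below. Let pT and pC be the response rates among baseline sPGA of 2 or more, and sT and sC the shares of the low-baseline subjects still at 0/1 at week 24 (retention). By randomisation, f is taken as equal in the arms.

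- Two-grade rate in an arm: (1 - f) × p. Difference: (1 - f)(pT - pC). Ratio: pT/pC, unchanged. Ceiling: 1 - f.
- 0/1 rate in an arm: (1 - f) × p + f × s, which is raised when s exceeds p. Difference: (1 - f)(pT - pC) + f(sT - sC). This is below pT - pC only if sT - sC < pT - pC.

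**Step 3: numbers.** Assume pT = 50% and pC = 30%, used for both endpoints for simplicity. The unmixed difference is 20 points and the ratio 1.67. Differences are in percentage points.

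| f | Two-grade rates | Difference (ratio) | 0/1 rates, all retained | Difference (ratio) | 0/1 difference, retention 90% vs 80% | 0/1 difference, retention 95% vs 70% |
|---|---|---|---|---|---|---|
| 5% | 47.5% vs 28.5% | 19.0 (1.67) | 52.5% vs 33.5% | 19.0 (1.57) | 19.5 | 20.3 |
| 10% | 45.0% vs 27.0% | 18.0 (1.67) | 55.0% vs 37.0% | 18.0 (1.49) | 19.0 | 20.5 |
| 20% | 40.0% vs 24.0% | 16.0 (1.67) | 60.0% vs 44.0% | 16.0 (1.36) | 18.0 | 21.0 |
| 30% | 35.0% vs 21.0% | 14.0 (1.67) | 65.0% vs 51.0% | 14.0 (1.27) | 17.0 | 21.5 |

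Any equal retention gives the same 0/1 difference. With 90% in both arms and f = 30%, the rates are 0.7 × 50 + 0.3 × 90 = 62% and 0.7 × 30 + 0.3 × 90 = 48%, again 14 points. In the last column the retention gap (25 points) exceeds the response gap (20 points), so nothing shrinks.

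**Step 4: other assumed rates.** At f = 30%, 40% vs 25% gives 0.7 × 15 = 10.5 points instead of 15, and 60% vs 30% gives 0.7 × 30 = 21 points instead of 30.

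**The case against.** The case for leaving the plan as it is has four parts.

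*The non-zero rule for LDI, SPARCC and mNAPSI, applied literally to sPGA, would remove only grade 0, which criterion 105 already makes rare.* This does not stand. For those endpoints the success criterion is a score of 0, so a non-zero baseline removes exactly the subjects who already meet it. For a criterion of 0 or 1, the condition that does the same work is a baseline of 2 or more.

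*The planned rate answers a fair question: who is at 0 or 1 at week 24 among all randomised subjects with a given BSA.* This stands. Randomisation keeps that arm comparison valid, so the matter is dilution and readability, not bias. It is a reason to allow the all-subject 0/1 rate alongside. It does not help the two-grade rate, which some subjects cannot achieve.

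*The categorical summary already shows the starting grades.* This stands in part. SAP 4.1.5 plans it at all visits other than week 24, and Protocol Table 1 schedules sPGA at week 0, so f could probably be read off. The two-grade rate could then be rescaled by 1/(1 - f), apart from missing data. The 0/1 rate among baseline 2 or more could not be recovered, because separate tables by visit do not cross baseline with week 24.

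*Nothing inferential depends on it.* This stands and limits the weight of the point.

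A reader might also infer that comparisons between BSA subgroups are confounded by baseline sPGA. The starting grade may well differ by BSA group, but no contrast or interaction test between those groups is planned for sPGA. Restricting to baseline 2 or more would still leave different mixes of grades 2 to 5.

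**Conclusion.** The point holds as a gap in how the denominators are defined. The documents allow subjects with baseline sPGA 1, and rarely 0, into every sPGA responder rate, most plausibly in the BSA < 3% group. How many there will be is not stated.

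Only one effect on the arm comparison is certain: if such subjects are present, the absolute two-grade difference is multiplied by 1 - f. Its ratio does not change. For 0/1, the rates are likely raised. The difference shrinks only if the arms differ less in keeping low-baseline subjects at 0/1 than in response among the rest. The 19 to 14 points in place of 20 rest on assumed rates of 30% and 50%, equal retention, and an assumed f of 5% to 30%.

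Two stronger readings are tempting and not supported. One is that these subjects are automatic successes on 0/1; they can worsen. The other is that the plan necessarily understates the skin effect or loses power. Shrinkage of 0/1 is conditional, and the SAP plans no sPGA test. The primary and key secondary results do not use sPGA. This is a cheap improvement to descriptive other secondary and exploratory summaries.

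**What to change.** Amend SAP 4.1.3, 4.1.5 and 10.5.2 before unblinding so that, within each BSA set:

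- sPGA 0/1 and two-grade improvement are reported in subjects with baseline sPGA of at least 2;
- one-grade improvement is reported in subjects with baseline sPGA of at least 1;
- baseline sPGA is tabulated by arm and BSA set;
- the 0-5 categorical summary stays for everyone, with the all-subject 0/1 rate beside it if wanted.

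List the change in SAP Section 11. Baseline sPGA is already collected on day 1, so no new data are needed. The cost is a smaller denominator for these rates, probably most noticeable in the BSA < 3% group. Fixing the rule now also avoids choosing a denominator after the data are seen, since Section 11 leaves room for later ad hoc analyses.
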